3.2 Hypotheses for Specific Outcomes

3.2.1 Indwell time

- 1) The duration of PIVC indwell time will be greater in duration for longer catheters.
- 2) The duration of PIVC indwell time will be greater for catheters of smaller gauge (larger bore).

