10.5 Primary Endpoint(s)

Comparisons across and between device configurations (i.e., length/gauge) will be made using logrank tests for indwell time. The primary endpoint will be evaluated using statistical modeling software (Prism, Release 8.3; GraphPad Software Inc., USA) or R (R 3.6.2 or higher).

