2.4 Sample Size

There is limited published data investigating the impact of PIVC catheter length on indwell time; a single article was found in the literature comparing catheter survival between a BD PIVC catheter (20 gauge; 4.78 cm/1.88-inch length) and midline catheter (POWERWAND™, 19.5 gauge; 6 cm/2.3-inch length). The indwell time results for this research were utilized to calculate a sample size estimate using the routine “Survival - Two Survival Curves - Logrank Tests” available in the software PASS 2019. Based on the available dataset, a sample size of ~20 participants per PIVC length would be required, considering median failure times of catheter of different lengths of 1 and 3 days, as can be seen in Figure 2.4.1. The same calculation will be applied to investigating the impact of increased gauge, because the increased volume of catheters is similar in both condition (i.e., 1 versus 1.75 inch = 75% increased volume; 20 versus 22 gauge = 51% increased volume).

Figure 2.4.1: Details of sample size calculation

Logrank Tests

Numeric Results for the Logrank Test in Terms of Sample Size

Alternative Hypothesis: Two-Sided

Power	N1	N2	N	Haz Ratio (HR)	Ctrl	Trt	Acc-rual Pat'n	Acc-rual Time/Total Time	Ctrl Loss	Trt Loss	Ctrl to Trt		Alpha	Beta
					Med Surv Time (M1)	Med Surv Time (M2)					to Trt	to Ctrl		
0.8054	19	20	39	0.3333	1.00	3.00	Equal	0 / 3	0.0000	0.0000	0.0000	0.0000	0.0500	0.1946

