5.2.1 Statistical Analysis of Primary Endpoint

5.2.1.1 Indwell Time

It is hypothesized that:

- PIVC indwell time will be greater for longer catheters
- PIVC indwell time will be greater for catheters of smaller gauge (larger bore)

In order to test these hypotheses, catheter indwell time will be assessed using survival analysis, including:

- Kaplan-Meier survival curves including Log-Rank test p-value
- Cox Proportional Hazards Model with Hazard Ratios for each device vs. default device condition (BD Nexiva 20G x 1 inch) and associated 95% Confidence Intervals. Effect of the following covariates will be investigated: gender, age, BMI and dominant arm.

Main analysis will be performed stratified by device, depending on the results pooled analyses by gauge or by catheter length might be performed. An example of the Kaplan-Meier curve and associated metrics is provided in Appendix B by Figure B.1.1. An example of the Hazard Ratios extracted from the Cox Proportional Hazards models is provided in Appendix A by Table A.4.2.

For the purpose of this survival analysis, device failure (inability to flush or draw blood, see section 6.6) will be identified as follows:

- Blood Draw: Variables DEBLDCS equal to “N” and DEBLDRS equal to “N” from table INBCINBC
- Flush: Variables DEFLSSU equal to “N” and DEFLSRS equal to “N” from table INFL

Failure can occur during any of the 7 repeats of the blood draw (for either tube volumes) or flush processes, as highlighted in orange on Table 2.7.1, for right or left arm, per randomization schedule. Date-time of failure is then given by the aggregation of variables DEDTN & DEFTM, from tables INBCINBC or INFL, respectively for blood draw or flush.

Additional Indwell Time summary statistics and graphical representation will be provided as represented in Appendix A by Table A.4.1 and in Appendix B by Figure B.2.1, respectively.

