5.2.4 General Considerations

- For categorical data, count and percentage with 95% confidence interval will be calculated.
- For continuous data, average, standard error, 95% confidence interval, median, inter-quartiles, minimum and maximum will be provided.
- p-values less than 0.05 will be considered statistically significant. Multiple comparisons adjustments (Tukey's or Sydak's) will be made when appropriate
- Importance of factors/variables might be evaluated using machine learning tools such as the Boruta algorithm (random forest all-relevant approach)

- Whenever possible, effects of the following covariates will be investigated: gender, age and BMI
- Initially, all factors/variables will be included into the model as well as any two-way/three-way interactions.
- Variables or interactions which are not significant ($p\text{-value} < 0.05$) will be removed from the final model. Models adjusted with significant effects (and significant interactions if any) will be used for analysis whenever possible.
- Use of models will be preferred to non-parametric tests whenever possible.
- Residual plots for each model will be drawn and reviewed to ensure there are no systematic patterns.
- Transformation of response and/or explanatory variables will be investigated whenever modeling assumptions are not satisfied.

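### The contrasts that match the two primary hypotheses across all catheters (length, gauge) are optional and decided after the by-device results are seen; they should be fixed in advance

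*SAP*

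**What the plan says.** Protocol 3.2.1 gives the first primary hypothesis as "The duration of PIVC indwell time will be greater in duration for longer catheters" and adds a second, that larger-bore catheters last longer. SAP 5.2.1.1 repeats both and presents its survival analysis as the test of them. That analysis consists of Kaplan-Meier curves with a log-rank p-value (groups not named) and a Cox model giving each device's hazard ratio against 20G x 1 inch. On pooling it says: "Main analysis will be performed stratified by device, depending on the results pooled analyses by gauge or by catheter length might be performed".

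Other places describe the primary analysis differently:

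- Protocol 10.5: "Comparisons across and between device configurations (i.e., length/gauge) will be made using logrank tests for indwell time". No condition is attached.
- Protocol 4.2 plans a paired analysis for length and an unpaired one for gauge.
- SAP 5.2.2.3 refers to the primary survival model as one whose variables are gauge and length.
- SAP 2.4 sizes a two-group log-rank test on length ("Alternative Hypothesis: Two-Sided", "median failure times of catheter of different lengths of 1 and 3 days") and concludes that about "20 participants per PIVC length would be required". It then applies the same calculation to gauge.

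On error control, SAP 5.2.4 says "p-values less than 0.05 will be considered statistically significant" and "Multiple comparisons adjustments (Tukey's or Sydak's) will be made when appropriate". It does not say which tests form a family. SAP 2.9 sets no acceptance criteria, and SAP 5.2 treats estimation and significance as about equally important.

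**The concern.** A stated rule makes the fullest test of each primary hypothesis depend on the data. An unconvincing by-device result can be followed by pooling, and a convincing one can be left alone. The reverse is also possible: a null by-device result with no pooling would set aside the most powerful test of the trial's own length hypothesis. The SAP gives no trigger, deciding contrast or order by which a reader could tell afterwards which path was the planned one.

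The choice also has to be made twice. Under SAP 2.6 an independent statistician runs the indwell-time analysis of 5.2.1.1 before database lock, for business decisions, while the lead statistician stays blinded to that output. The two could resolve the optional clause differently, and nothing in the SAP would settle which was right.

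**Working it through.** **1. What the committed tests compare.** There are 40 participants with two catheters each, so 80 catheters, 20 per device.

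| Committed comparison | What it isolates |
|---|---|
| Log-rank over four devices | neither factor (any difference) |
| 20G x 1.75 v 20G x 1 | length, within 20G (devices holding 40 of 80 catheters) |
| 22G x 1 v 20G x 1 | gauge, at 1 inch (40 of 80) |
| 22G x 1.75 v 20G x 1 | both factors mixed |

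Length within 22G and gauge at 1.75 inch have no direct contrast. (Mock Table A.4.2 takes 22G x 1 inch as reference. It is only a layout, but the reference should be made consistent.)

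**2. The plan's own figure.** From SAP 2.4: N = 19 and 20, medians 1 and 3 days, 3 days of follow-up, no losses, two-sided 0.05. Expected events = 19(1 - 0.5^3) + 20(1 - 0.5) = 16.625 + 10 = 26.625. Schoenfeld: sqrt(26.625 x 19/39 x 20/39) x ln 3 - 1.96 = 2.833 - 1.96 = 0.873, power 0.809, against 0.8054 stated. The Lakatos method gives 0.806. The sizing is therefore for a two-group comparison, the type of test that 5.2.1.1 makes optional across gauges.

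**3. False positives under no effect.** The documents give neither a common median nor a within-person correlation, so these are assumed: exponential failure times, median 48 h, censoring at 72 h, Gaussian-copula correlation, ordinary unpaired log-rank and Wald tests. Percentage of simulated trials with p<0.05 (10,000 runs in the 0 and 0.3 columns, except that the two single-test rows used 3,000; 3,000 runs throughout at 0.6):

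| Tests counted | corr. 0 | corr. 0.3 | corr. 0.6 |
|---|---|---|---|
| Four-group + three hazard ratios + two pooled, any | 17.3 | 15.6 | 14.0 |
| Three hazard ratios, any | 12.2 | 10.2 | 8.1 |
| Two pooled tests, any | 10.1 | 10.8 | 11.5 |
| Pooled length alone | 4.9 | 2.4 | 0.7 |
| Pooled gauge alone | 4.7 | 8.4 | 10.8 |
| Pooled tests only after a significant four-group test | 4.0 | 3.9 | 3.8 |

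Smaller separate runs over correlations 0 to 0.5 put the first row at 14-19% and the third at 9-12%. Simulation error near 16% is sqrt(0.16 x 0.84/1,500) = 0.9 points for 1,500 runs and 0.4 points for 10,000. Over medians of 24 to 72 h and other readings of the SAP, up to all six pairwise tests plus the global and pooled tests, the range is about 3-24%.

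Two independent tests at 0.05 would give 1 - 0.95^2 = 9.75%. As correlation rises, much of the pooled-pair figure comes from the gauge log-rank ignoring that two catheters share a participant: that test alone rejects about 8% at 0.3 and 10-11% at 0.5. A Sidak correction of the unpaired pair does not remove this (4.7%, 6.0% and 7.3% at correlations 0, 0.3 and 0.6).

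**4. What is lost if pooling is not done.** Take a length hazard ratio of 0.5 (assumed; the plan uses 0.33) and a 1-inch median of 1 day. By Schoenfeld, with independent catheters:

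- Within one gauge: events = 20(0.875) + 20(1 - 0.5^1.5) = 30.43; sqrt(30.43/4) x 0.693 - 1.96 = -0.05; power 48%.
- Pooled: events = 60.86; sqrt(60.86/4) x 0.693 - 1.96 = 0.74; power 77%.

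Simulation agrees: 45-51% within one gauge, 59-66% for the four-group test and 76-82% pooled. In about 19% of such trials the pooled length test was significant and the four-group test was not. At the planned 0.33 the simulated figures are 83%, 96% and 99%.

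**The case against.** A reader might infer that the plan has a family-wise false-positive rate of 15-17% against a stated 5%. The documents do not support that. The rate is not a property of this SAP: it requires that all six tests are run, that none is adjusted and that any one counts as success. The SAP only says pooling might be done, allows Tukey or Sidak adjustment, and defines no success criterion. If pooling followed only a significant four-group test, the rate would be about 4%. The 0.05 in SAP 5.2.4 is a threshold for each test, and no family-wise claim is made anywhere.

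A reader might also infer that the committed analysis leaves both hypotheses untested. That goes too far. Two of the three hazard ratios address length and gauge directly, though at one level of the other factor, and at the planned hazard ratio a comparison within one gauge has about 83% power.

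The study is also described as a feasibility study giving preliminary signals (Protocol 4.1), exploratory (Protocol 10.2) and not for registration (Protocol 14.2). This lowers the stakes but does not remove the point. SAP 5.2 still gives significance weight alongside estimation, Protocol 4.1 ties the results to decisions on product development, and the adjustment clause cannot help when the number of tests is itself left open.

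**Conclusion.** The point holds as a matter of pre-specification. SAP 5.2.1.1 makes the all-catheter test of each primary hypothesis data-dependent, and it does not agree with Protocol 10.5, Protocol 4.2 or SAP 5.2.2.3. The consequence is selective or unclear reporting of the primary result, not the failure of a confirmatory error guarantee. The error rates are illustrations under the assumed median, correlation and family of tests, and their width reflects how much the SAP leaves open. The power loss is material at a hazard ratio of 0.5 and modest at the planned 0.33. This should be changed before the data are analysed.

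**What to change.** In SAP 5.2.1.1, delete the clause that makes pooling optional and write, for example:

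> The primary contrasts are 1.75 v 1 inch over both gauges and 20G v 22G over both lengths. Both are always performed and reported with hazard ratios and 95% confidence intervals, from a Cox model with length and gauge terms and participant-clustered robust standard errors. The four-device curves, log-rank p-value and hazard ratios are supportive.

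Another method that accounts for two catheters per participant would also serve. Protocol 10.5 and 4.2 and SAP 5.2.2.3 should then be aligned with the choice, and the preliminary analysis in SAP 2.6 should follow the same text.

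State also how the two tests share the 5% level. Sidak across the two is one way, with each at 1 - sqrt(0.95) = 0.0253. A fixed order is another. Length first is defensible, since Protocol 2.2 names length and the sample size was computed for it, but it is not the only choice: SAP 1.1 names both factors and SAP 2.4 extends the calculation to gauge.

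The cost is wording, plus by-device p-values that become supportive. With Sidak, pooled power at a hazard ratio of 0.5 falls from 77% to 68% (2.704 - 2.236 = 0.468), and at 0.33 from 98% to 97% (4.074 - 1.960 = 2.114; 4.074 - 2.236 = 1.838), by the Schoenfeld formula with independent catheters. A fixed order avoids this loss for the first contrast but makes a claim on the second depend on it.

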4 STUDY DESIGN

4.1 Overall Design

This is a randomized, single-center, open-label feasibility trial to provide preliminary signals of performance to help make decisions about whether to continue with the development of product enhancements. Four variations of the BD Nexiva PIVC (20G x 1, 20G x 1.75, 22G x 1, or 22G x 1.75) will be placed in the lower cephalic vein of both arms in approximately 40 healthy volunteers; 20 participants with 20G x 1 inch and 20G x 1.75 inch catheters, and second group of 20 participants with 22G x 1 inch and 22G x 1.75 inch catheters. PIVC indwell time will be monitored (removal at 72 hrs or upon inability to flush/aspirate) with blood collected by venipuncture (Day 1 only) and via the devices using 2 and 6mL vacutainers throughout the remainder of indwell time.

After 5 participants have completed their final visit, the in-situ catheter positions will be compared to the expected tip position based on the catheter lengths (1 inch versus 1.75 inch for either gauge). Tip position of the longer catheter is expected to reside more horizontally within the vessel. In the event catheter tip position differences are not distinct between catheter device lengths study conduct may be stopped. Additionally, this analysis will be used to refine study logistics associated with device placement, securement, sonographic measurements, and blood sample acquisition/testing over the 72-hour study duration.

Each participant will complete 6 visits: a Screening Visit (V1), followed by 4 Visits (V2-V5) to be started within 30 days after screening, and a 24-96 hour follow-up post catheter removal (V6).

The duration of the study execution is expected to be 5 months.

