7.4 Image acquisition of indwelling catheter and cephalic vein

The insertion loci will be assessed prior to, and immediately after, insertion of the PIVC using clinically approved ultrasound with a wide-band, high frequency linear array probe from which all B-Mode, color-flow (CF), and pulse wave doppler (PWD) images will be acquired. At each visit prior to flushing and blood collection the following images will be recorded: a) three cross-sectional, B-mode images with the indwelling PIVC in view; b) three cross-sectional, B-mode images proximal to the PIVC tip; c) three longitudinal, B-mode images encompassing close to the insertion point of the PIVC to beyond the PIVC tip; and d) a 15 s longitudinal, PWD-CF duplex cine loop with the sample volume set ~1cm proximal to the PIVC tip. The sampling frequency for all images will be chosen high enough to avoid frequency aliasing. Coded harmonic imaging will be utilized for all images to improve visual clarity via enhancement of near-field resolution.

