7.6 PIVC-Failure

The definition of PIVC failure in the current study will be defined as: 1) an inability to flush or collect blood through the PIVC or 2) removal of the PIVC based on medical doctor's assessment of an AE. A device rescue decision tree will be utilized to identify if the PIVC has failed.

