1.2 Objectives

1.2.1 Primary Objectives

To assess patent indwell time for PIVCs of different length and gauge.

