2.8 Endpoints

2.8.1 Primary Endpoint

The primary endpoint is the catheter indwell time, defined as the time from catheter insertion to time of catheter failure. It is measured in hours.

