6.6 Device Failure, Malfunctions and Defects

PIVC failure in the current study is defined as:

1. An inability to flush or collect blood through the PIVC
2. The removal of the PIVC based on medical doctor's assessment of an AE

A device rescue decision tree (see Appendix 16.5 of the study protocol) will be utilized to identify if the PIVC has failed.

7 Safety Analysis

Sufficient detail on summarizing safety data, e.g., information on severity, expectedness, and causality; details of how adverse events are coded or categorized; how adverse event data will be analyzed is provided in a separate document (i.e., a safety management plan).

8 Interim Analysis Plan

No interim analysis has been planned.

9 References

- [1] R Core Team. *R: A Language and Environment for Statistical Computing*. R Foundation for Statistical Computing, Vienna, Austria, 2016. URL <https://www.R-project.org/>.
- [2] Miron B. Kursa and Witold R. Rudnicki. Feature selection with the Boruta package. *Journal of Statistical Software*, 36(11):1–13, 2010. URL <http://www.jstatsoft.org/v36/i11/>.

10 SAP Revision History

Version Number	Rationale for Change	Section or Page Affected	Description of Change
1.0	Original SAP		

11 Appendix

A Tables

A.1 Demographics

Table A.1.1: Numerical Summary of Subjects Demographics, per Group (i.e. Gauge) and Overall

Characteristic	20G	22G	Overall
Age (years)			
Mean	42.35	39.87	41.11
95% Mean CI	37.42, 47.07	34.77, 44.98	37.51, 44.70
Median	45.15	39.45	42.15
SD	11.22	12.14	11.61
Min, Max	24.2, 56.3	23.9, 57.4	23.9, 57.4
Total Count	20	20	40
Gender			
F	11 (55.0%)	9 (45.0%)	20 (50.0%)
M	9 (45.0%)	11 (55.0%)	20 (50.0%)
Total	20	20	40
Ethnicity			
Non Hispanic / Latino	18 (90.0%)	19 (95.0%)	37 (92.5%)
Hispanic / Latino	2 (10.0%)	1 (5.0%)	3 (7.5%)
Total	20	20	40
Race			
Asian	6 (30.0%)	8 (40.0%)	14 (35.0%)
Other	7 (35.0%)	6 (30.0%)	13 (32.5%)
White / Caucasian	7 (35.0%)	6 (30.0%)	13 (32.5%)
Total	20	20	40
Height (cm)			
Mean	166.06	168.64	167.35
95% Mean CI	161.10, 171.26	163.55, 173.65	163.63, 171.10
Median	161.05	168.20	166.65
SD	12.09	11.78	11.85
Min, Max	151.2, 185.6	150.4, 188.6	150.4, 188.6
Total Count	20	20	40
Weight (kg)			
Mean	67.92	76.78	72.34
95% Mean CI	63.44, 72.27	73.23, 80.32	69.18, 75.43
Median	72.50	76.10	74.75
SD	10.41	8.34	10.34
Min, Max	52.8, 81.6	63.5, 88.7	52.8, 88.7
Total Count	20	20	40
BMI (kg/m²)			
Mean	22.40	22.90	22.65
95% Mean CI	21.25, 23.55	21.85, 24.00	21.88, 23.45
Median	23.00	23.50	23.00
SD	2.68	2.55	2.60

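### SAP 5.2.1.1 takes the primary event only from flush and blood-draw records, although SAP 6.6 and Protocol 7.6 also count removal for an adverse event as catheter failure

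*SAP*

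**What the plan says.** **Endpoint.** SAP 2.8.1 gives indwell time in hours, "defined as the time from catheter insertion to time of catheter failure".

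**Definition of failure.** Protocol 7.6 has two parts: "an inability to flush or collect blood through the PIVC or 2) removal of the PIVC based on medical" (the sentence continues to a doctor's assessment of an AE). SAP 6.6 repeats both; its second item begins "The removal of the PIVC based on medical" and ends the same way.

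**Event coding.** SAP 5.2.1.1 says "device failure (inability to flush or draw blood, see section 6.6) will be identified as follows". Two rules follow: a pair of draw variables both equal to N in table INBCINBC, or a pair of flush variables both equal to N in table INFL. On timing, "Date-time of failure is then given by the aggregation of variables" DEDTN and DEFTM, taken from those same two tables. No removal or AE field is named.

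**Removal reasons.** SAP 5.2.3.1 lists Adverse Event as a reason for removal, separate from Flush Failure and Blood Draw Failure, but only for an exploratory frequency summary.

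**Text that points the other way.** Protocol 4.1 describes "removal at 72 hrs or upon inability to flush/aspirate", and SAP 1.2.1 states the primary objective as "To assess patent indwell time for PIVCs of different length and gauge". Neither mentions AE removal.

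**Censoring.** No rule is written for a catheter that leaves before 72 h without an event.

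**The concern.** A programmer who follows SAP 5.2.1.1 has no field that could turn an AE removal into an event. If a failed flush or draw is also on record, the catheter still counts. If not, it is a failure under SAP 6.6 and Protocol 7.6 and a non-event in the primary analysis.

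The schedule leaves room for that case. Protocol 7.4 says "At each visit prior to flushing and blood collection the following images will be recorded", and Protocol 7.10.1 has a nurse inspect the site before each draw and refer to the study doctor at a phlebitis score of 4 or more. A complication can therefore be found before that visit's flush or draw is attempted.

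At stake is which event the primary Kaplan-Meier curve, log-rank test and Cox model describe. SAP 5.2 gives absolute effects about the same weight as significance, so the level of the curve matters as well as the contrast. The preliminary analysis in SAP 2.6 uses the same derivation before database lock, to inform business decisions.

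**Working it through.** **1. The passages side by side**

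| Situation of the catheter | SAP 6.6 / Protocol 7.6 | SAP 5.2.1.1 coding |
|---|---|---|
| Failed, unrescued flush or draw | failure | event |
| AE removal, failed flush or draw also on record | failure | event |
| AE removal, no failed flush or draw on record | failure | not an event |
| Leaves before 72 h for another reason, no failed flush or draw | not a failure | not an event; censoring time not stated |

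The third row is the contradiction and the fourth is the gap. The mock listing in SAP Table C.0.5 is consistent with both. Of its 40 rows, 22 are events (13 flush, 5 draw 2 mL, 4 draw 6 mL) and 18 have status 0, of which 9 end before 72 h with no reason shown. These are dummy data, so they show only what the template expects.

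**2. The plan's own figure.** Inputs from SAP 2.4: 19 and 20 catheters, medians of 1 and 3 days, 3 days of follow-up, hazard ratio 0.3333, two-sided alpha 0.05, power 0.8054.
- Failure-free at 72 h: 0.5³ = 12.5% and 0.5¹ = 50%.
- Expected events: 19 × 0.875 + 20 × 0.50 = 26.6.
- Schoenfeld: z = √26.625 × ln 3 / 2 − 1.96 = 2.83 − 1.96 = 0.87, power 0.809. The Lakatos method gives 0.806.

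The stated power is reproduced, so the planned failure-free levels can be used below.

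**3. Effect of one recoded catheter.** Assume 20 catheters in a configuration, no other censoring before 72 h, and the AE removal censored at removal. If n are at risk at that time, including the catheter itself, then

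coded S(72) = defined S(72) × n/(n − 1).

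| Defined S(72) | Failures | First to leave (n = 20) | Last to leave | Mean over positions | SE = √(S(1 − S)/20) |
|---|---|---|---|---|---|
| 50% (10 of 20) | 10 | 0.50 × 20/19: +2.6 points | n = 11, 0.50 × 11/10: +5.0 | +3.6 | 11.2 points |
| 15% (3 of 20, near 12.5%) | 17 | 0.15 × 20/19: +0.8 points | n = 4, 0.15 × 4/3: +5.0 | +1.8 | 8.0 points |

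**4. Direction for the length comparison.** The documents give no AE-removal rate, so these shares are assumptions. Suppose a share of failures are AE removals that the coding misses.
- Equal share in both lengths: the hazard ratio stays at 0.33 and events are lost. At 5% there are 25.3 events (power 0.79); at 10%, 24.0 (0.77); at 30%, 18.6 (0.66).
- 20% in the 1-day-median group only: 0.333/0.8 = 0.42.
- 20% in the 3-day-median group only: 0.333 × 0.8 = 0.27.

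The shift can go either way.

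**The case against.** The strongest reply is that the narrower event is deliberate. SAP 5.2.1.1 limits its definition to the survival analysis, the objective speaks of patent indwell time, Protocol 4.1 mentions only flush and aspiration, and AE removals are tabulated in SAP 5.2.3.1. If loss of patency is the target and AE removal is independent of it, censoring those removals is not biased. That reading is fair. It does not settle the matter, because SAP 2.8.1 times the endpoint to failure, SAP 5.2.1.1 itself points to 6.6, and both 6.6 and Protocol 7.6 include AE removal.

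A second reply is that the gap may seldom arise. The flush and draw failure modes in the SAP mock tables include thrombus, infiltration and dislodgement, so many complications may already be recorded as failed flushes or draws. The case report form is not in the documents, so it cannot be seen how a flush or draw skipped because of an AE would be entered. This stands, and it is why no total effect is claimed.

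A third reply is that the arithmetic censors at removal, while an earlier censoring time would give a larger n. That is correct, but n cannot exceed 20, so the shift stays within the ranges shown.

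Stronger readings that the documents do not support:
- *Patency itself is overstated.* What is overstated is freedom from the two-part failure. A catheter removed while still patent has not lost patency.
- *The Evaluable population changes.* Protocol 10.3 refers to catheter failure, which Protocol 7.6 already defines to include AE removal. The survival coding does not alter that.
- *The rule on thrombi over 5 cm (Protocol 7.4.5) and removal without data collection (Protocol 8.1) show the gap in action.* Both concern a participant leaving the study and are not clearly AE removals in the sense of 7.6.

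**Conclusion.** The point holds as a contradiction between the definition of the primary event and the rule that codes it, together with a missing rule for early censoring. Measured against SAP 6.6 and Protocol 7.6, the coding overstates failure-free indwell time.

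The size is limited and partly unknown. One missed AE removal among 20 catheters moves the 72 h estimate by 2.6 to 5.0 points at 50% failure-free, or 0.8 to 5.0 points at 15%, in each case less than one standard error. This rests on no other censoring and on censoring at removal. How many such removals will occur, and which length they would favour, cannot be told from the documents. A reader might infer a bias in favour of one length; nothing in the text supports that.

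This is a feasibility study with no acceptance criteria (SAP 2.9), which limits the consequence. It should still be fixed, because it concerns the primary event and costs little. That the text contradicts itself is certain; its practical effect is not.

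**What to change.** Choose one reading and write it in every place.

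- **To match SAP 6.6 and Protocol 7.6:** in SAP 5.2.1.1, add removal with reason Adverse Event (already planned in 5.2.3.1) and its date-time to the event derivation. Apply it per catheter, so that the event belongs to the catheter the AE concerns. Keep flush/draw-only failure, with AE removal censored, as a sensitivity analysis.
- **If loss of patency alone is intended:** say so in SAP 2.8.1, SAP 6.6 and Protocol 7.6, and treat AE removal as censored or as a competing event.

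Under either reading, state how catheters that leave before 72 h without an event are censored, and at what time (for example removal, or the last successful flush and draw). Settle this before the SAP 2.6 preliminary analysis, so that the definition is fixed before anyone sees results by device.

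An analysis of removal for any cause would be a reasonable extra, since fewer dislodgements is part of the length rationale in Protocol 4.2, but this point does not require it.

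The cost is a few SAP sentences, a Protocol clarification under the second reading, and slightly more analysis work. Under the first reading the event is a composite of lost patency and AE removal, which the sensitivity analysis separates.
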